#### 7.1.3. Treatment Phase

#### 7.1.3.1. Days 0 to 6

On the morning of Day 0 of the Treatment Phase, subjects will receive one of the following treatments (based on randomization in a 1:1 ratio, stratified by gender) to:

- Group A: CAM2038 q1w 24 mg SC injection
- Group B: CAM2038 q1w 32 mg SC injection

Maintenance IR morphine 30 mg will be withheld for at least 12 hours prior to CAM2038 q1w dosing; therefore, the Day -1 evening dose and the Day 0 morning dose of IR morphine 30 mg will be withheld. The Clinical Opiate Withdrawal Scale (COWS; See Section 17.2) will be administered prior to dosing with CAM2038 q1w; in order to be dosed on Day 0, subjects will be required to have a COWS score of  $\geq 8$ , indicative of mild withdrawal.

CAM2038 q1w treatment will be administered at approximately 9:00 am; CAM2038 q1w administration instructions for user (IFU) will be provided in the Manual of Procedures (MOP).

On Days 1 to 3 and Days 4 to 6, subjects will undergo 2 separate Hydromorphone Challenge Sessions (described in Section 7.1.4), with each daily challenge dose of IM hydromorphone administered at approximately 9:00 am (i.e., approximately 24, 48, 72, 96, 120, and 144 hours following Day 0 CAM2038 q1w injection). Safety and pharmacodynamic assessments will be conducted immediately following each dose of hydromorphone administered in each Hydromorphone Challenge Session (maximum 5 hours after Hydromorphone Challenge Session). Plasma samples will also be collected prior to hydromorphone dosing on each day of the Hydromorphone Challenge Sessions.

#### 7.1.3.2. Days 7 to 14:

On the morning of Day 7 (approximately 9:00 am) of the Treatment Phase, each Group (A and B) will receive a second dose of CAM2038 q1w according to their assigned treatment group. On Days 8 to 10 and Days 11 to 13, subjects will undergo 2 separate Hydromorphone Challenge Sessions, with each daily challenge dose of IM hydromorphone administered at approximately 9:00 am (i.e., approximately 24, 48, 72, 96, 120, and 144 hours following Day 7 CAM2038 q1w injection). As in previous sessions, each Hydromorphone Challenge Session will consist of subjects receiving 3 doses of IM hydromorphone (0 mg [placebo], 6 mg and 18 mg) in a

Version: 2.0, 17NOV2015 Page 34 of 99

randomized, crossover manner. Safety and pharmacodynamic assessments will be conducted immediately following each dose of hydromorphone administered in each Hydromorphone Challenge Session (maximum 5 hours after Hydromorphone Challenge Session).

Subjects will be discharged on Day 14, if medically acceptable according to the investigator or designee.

#### 7.1.4. Hydromorphone Challenge Sessions

Each Hydromorphone Challenge Session in the Qualification Phase and Treatment Phase will consist of the injection of 3 doses of IM hydromorphone 10 mg/mL (0 mg [placebo], 6 mg and 18 mg) administered once daily over 3 consecutive days in randomized order. Subjects will be randomized in a 1:1:1:1:1 ratio to 1 of 6 treatment sequences according to two 3 × 3 William squares. The following treatment sequences will be used: ABC, ACB, BAC, BCA, CAB, and CBA, where A, B, and C are IM Hydromorphone Challenge Sessions with 0 mg (placebo), 6 mg, and 18 mg, respectively. The volume of the 0 mg and 6 mg doses of IM hydromorphone will be the same as the volume of the 18 mg hydromorphone dose. Safety and pharmacodynamic assessments will be performed immediately following each dose of hydromorphone administered on each day of the Hydromorphone Challenge Session for a maximum 5 hours after Hydromorphone Challenge Session. Plasma BPN and norbuprenorphine levels will also be obtained approximately 60 minutes prior to hydromorphone dosing on each day of the Hydromorphone Challenge Sessions. After each dose of hydromorphone, subject's oxygen saturation, respiratory rate, and overall safety profile will be reviewed by the research/nursing staff (as described in Section 7.1.2.1) to determine whether it is safe to proceed with administration of the next dose of hydromorphone.

### 7.1.5. Follow-up Phase

Following the last day of the Treatment Phase (i.e., Day 14), plasma BPN levels are expected to be approximately 1.4 to 1.8 ng/mL and to gradually taper off; therefore, subjects are not expected to experience immediate withdrawal effects at the time of discharge. A follow-up telephone interview will be conducted approximately 7 days after discharge from the CRU to obtain information on any safety issues including withdrawal effects.

Subjects will participate in the study for approximately 7 weeks, from Screening to Follow-up.

An overview of the study design is provided in Figure 2.

Study assessments and procedures will be performed at the visits and time points outlined in the Schedule of Assessments.

Section 10 provides additional information on the baseline, safety, and pharmacodynamic procedures and assessments included in the study. Pharmacodynamic endpoints are described in Section 10.7. Statistical analysis is described in Section 12.

Version: 2.0, 17NOV2015 Page 35 of 99

Figure 2 Overview of Study Design

Screening	Qualif	ication		Treat	ment		Follow-up
	Inpatient Start	Qualification/ Baseline Challenge	q1w Dose 1	Week 1: Q1w Challenge	q1w Dose 2	Week 2: Q1w Challenge	
			CAN	Challenge 1: Days 1 to 3 Challenge 2: Days 4 to 6 2038 q1w 32mg		Challenge 3: Days 8 to 10 Challenge 4: Days 11 to 13 Discharge: Day 14	
	MS-IR (QID)	morning of the Qual	CAN	12038 q1w 24 mg			
		Challenge					
2 weeks	Day -10, Day -9, Day -8, Day -7, or Day -6 to Day -4	Days - 3 to -1	Day 0	Days 1 to 6	Day 7	Days 8 to 14	Day 21

IR = immediate-release; MS = morphine sulfate; q1w = once weekly dosing; R = randomization

**Table 4** Schedule of Assessments

Screening		Inpatient Qualification Phase				Follow-up Phone Call				
Visit:	1 2									
Day:	-39 to -11	-10, -9, -8, -7, OR -6	-9, -8, -7, -6, OR -5 to -4	-3 to -1	0	1 to 3 & 4 to 6	7	8 to 10 & 11 to 13	14/ ET	21
Assessment										
Informed Consenta	X									
Eligibility Criteria Review b	X	X								
Medical and Medication History	X	Xc								
DSM-V	X									
Physical Examination (including BMI)	X d	Xe							Xe	
Serology panel (optional)	X									
Concomitant Meds/Procedures	X	X	X	X	X	X	X	X	X	X
ECG	X	X			Xf		Xf		X	
Urine Drug Screen g	X	X								
Breath Alcohol Test	X	X								

<sup>a Subjects must voluntarily provide written informed consent prior to any study-related procedures being performed.

Version: 2.0, 17NOV2015 Page 37 of 99

<sup>b Prior to enrollment in the Qualification Phase of this study, all Inclusion and Exclusion criteria must be met.

<sup>o Brief update on the subject's medical and medication history since Screening at inpatient check-in only.

<sup>d A complete physical exam of all major body systems will be performed during Screening including height, weight and BMI.

<sup>e Abbreviated (symptom-directed) physical examination performed at the investigator's discretion (height will not be measured)

f ECGs performed prior to dosing with CAM2038 q1w

g Urine drug screen will be administered at Screening and inpatient check-in. Additional urine drug screens may be performed at the investigator's discretion.

	Screening	Inpatie	Inpatient Qualification Phase			Inpatient Treatment Phase				
Visit:	1				2					
Day:	-39 to -11	-10, -9, -8, -7, OR -6	-9, -8, -7, -6, OR -5 to -4	-3 to -1	0	1 to 3 & 4 to 6	7	8 to 10 & 11 to 13	14/ ET	21
Pregnancy Test	X h	X h		Xi	Xi		Xi			
FSH Test j	X									
Laboratory Tests k	X	X							X	
Pulse Oximetry/Cardiac monitoring/Respiratory Rate Monitoring		X 	X	X m	X	X m	X	X m		
Vital Signs n	X	X	X	X°	Xp	X°	X p	X°	X	

h A serum pregnancy test will be performed for all females of childbearing potential during Screening and at inpatient check-in. Following inpatient check-in and throughout the duration of confinement, urine pregnancy tests may be administered at the Investigator's discretion.

Version: 2.0, 17NOV2015 Page 38 of 99

A urine pregnancy test will be performed for all females of child-bearing potential only prior to IM hydromorphone injection on Day -3 and prior to dosing with CAM2038 q1w on Day 0 and Day 7.

<sup>j If post-menopausal females do not have a record of a FSH test, post-menopausal females will have a FSH test at Screening.

<sup>k Includes chemistry, hematology, urinalysis and coagulation profile.

Before each scheduled IR morphine 30 mg dose is administered, research/nursing staff will record oxygen saturation and respiratory rate and assess the subject for sedation and/or intoxication. If respiratory rate drops to <12 breaths per minute or oxygen saturation is <95%, the measurements will be repeated and recorded. If either oxygen saturation or respiratory rate remains outside parameters or the subject appears sedated or intoxicated, the oral maintenance dose will be withheld and a study Investigator notified. The withheld dose may be administered later (and the administration time recorded) once it is determined that the subject's status has returned to within a safe range. Continuous pulse oximetry and telemetry can be implemented at the Investigator's discretion.

m Pulse oximetry/Cardiac monitoring/Respiratory rate monitoring will be included on each Hydromorphone Challenge Session day (i.e., Days -3, -2, -1, 1, 2, 3, 4, 5, 6, 8, 9, 10, 11, 12, and 13). Monitoring will be continuous from pre-dose up to 5 hours post-dose or longer, if clinically indicated. After each dose of hydromorphone, subject's oxygen saturation, respiratory rate, and overall safety profile will be reviewed by the research/nursing staff to determine whether it is safe to proceed with administration of the next dose of hydromorphone.

<sup>n Includes temperature, blood pressure, pulse rate, respiratory rate.

On each Hydromorphone Challenge Session day (i.e., Days -3, -2, -1, 1, 2, 3, 4, 5, 6, 8, 9, 10, 11, 12, and 13), vital signs will be collected predose and at 15, 30, 45, 60, 90, 120 and 180 minutes post-dose and then hourly up to 5 hours post-dose.

P On CAM2038 q1w dosing days (i.e., Days 0 and 7), vital signs will be collected at pre-dose and at 15, 30, and 60 minutes post-dose, then hourly up to 6 hours post-dose.

	Screening	Inpatie	Inpatient Qualification Phase			Inpatient Treatment Phase				
Visit:	1				2					
Day:	-39 to -11	-10, -9, -8, -7, OR -6	-9, -8, -7, -6, OR -5 to -4	-3 to -1	0	1 to 3 & 4 to 6	7	8 to 10 & 11 to 13	14/ ET	21
Adverse Events q	X	X	X	X	X	X	X	X	X	X
C-SSRS (baseline/screening)	X									
C-SSRS (since last visit) r			X		X		X		X	
MADRS s	X		X		X		X		X	
COWSt	X	X	X	X	Xu	X	X u	X	X	
oows				X	Xu	X	X u	X	X	
CAM2038 Injection Site Examination					X	X	X	X	X	
Oral IR Morphine 30 mg Dosing v		X	X	X						
CAM2038 q1w SC Injection w					X		X			
Hydromorphone Challenge Session x				X		X		X		

<sup>q Any spontaneously reported adverse events will be recorded after the subject signs the informed consent form.

Version: 2.0, 17NOV2015 Page 39 of 99

<sup>r C-SSRS (since last visit) will be administered on Day -4, prior to dosing with CAM2038 q1w on Day 0 and Day 7, and prior to discharge on Day 14/ET.

<sup>s MADRS will be administered at Screening, Day -4, prior to dosing with CAM2038 q1w on Day 0 and Day 7, and prior to discharge on Day 14/ET.

<sup>t COWS will be administered on each CAM2038 q1w dosing day, prior to dosing. In order to be dosed on Day 0, subjects must have a COWS score ≥ 8. If opioid withdrawal occurs after dosing with CAM2038 q1w (precipitated withdrawal), COWS and OOWS will be collected every 4 hours while the subject is awake for at least 24 hours after dosing. COWS and OOWS will be administered prior to dosing on each Hydromorphone Challenge Session day.

<sup>u COWS and OOWS will be administered prior to dosing on each Hydromorphone Challenge Session and as needed, if a subject experiences precipitated withdrawal following administration of CAM203 q1w.

Very Subjects will be given a short-acting oral opioid, IR morphine 30 mg, QID, for a minimum of 3 days and a maximum of 7 days prior to the Qualification/Baseline Hydromorphone Challenge Session. One additional dose of IR morphine 30 mg may be administered for the first 3 days of stabilization, as needed, at the investigator's discretion. Subjects will not receive their dose of oral IR morphine 30 mg for approximately 12 hours prior to dosing with CAM2038 q1w on Day 0.

w Subjects will be dosed with either CAM2038 q1w 24 mg or 32 mg SC injection depending on the subject's treatment group assignment. A second dose of CAM2038 q1w will be administered on Day 7.

x Subjects will be scheduled to receive 3 doses of hydromorphone (0 mg [Placebo], 6 mg, and 18 mg) in a randomized crossover manner over 3 consecutive days.

	Screening	Inpatient Qualification Phase			Inpatient Treatment Phase					Follow-up Phone Call
Visit:	1				2					
Day:	-39 to -11	-10, -9, -8, -7, OR -6		-3 to -1	0	1 to 3 & 4 to 6	7	8 to 10 & 11 to 13	14/ ET	21
Pharmacokinetic sampling					Xy	X z	$X^{y}$	X z	Xaa	
Pharmacodynamic training/practice		Xbb								
VAS cc				X		X		X		
Severity of Opioid Withdrawal VAS					X dd		X			
Check-in		X								
Discharge									Xee	

BMI=body mass index; COWS=Clinical Opiate Withdrawal Scale; C-SSRS=Columbia-Suicide Severity Rating Scale; DSM-V = Diagnostic and Statistical Manual of Mental Disorders – Fifth Edition; ECG=electrocardiogram; ET=Early Termination; FSH=Follicle Stimulating Hormone; HIV= Human Immunodeficiency Virus; MADRS=Montgomery-Asberg Depression Rating Scale; OOWS=Objective Opioid Withdrawal Scale; PD=pharmacodynamic VAS=visual analog scale.

- y Blood samples will be taken pre-dose and 1, 4, 6 and 8 hours after CAM2038 q1w injection
- z Blood samples will be taken approximately 60 minutes prior to administration of hydromorphone on each of the 3 Hydromorphone Challenge Session days during the Treatment Phase (i.e., Days 1, 2, 3, 4, 5, 6, 8, 9, 10, 11, 12, and 13).
- aa Blood samples will be taken approximately 168 hours after CAM2038 q1w injection
- bb Pharmacodynamic training may be administered as frequently as required, but all subjects must complete at least one training session prior to the Qualification/Baseline Hydromorphone Challenge Session. Training can only occur prior to or after, but not during the Hydromorphone Challenge Sessions.
- cc On Hydromorphone Challenge Session days (i.e., Day -3, -2, -1, 1, 2, 3, 4, 5, 6, 8, 9, 10, 11, 12, and 13), subjective measures (Drug Liking, Feeling High, Any Drug Effects, Good Drug Effects, Bad Drug Effects, Sedated, Desire to Use Opioids VAS) assessments will be performed at predose (up to 15 minutes prior to dosing) and at 5, 10, 15, 30, 45, 60, 75, 90, 120, 150, 180, 210, 240, 270 and 300 minutes post-dose.
- dd Severity of Opioid Withdrawal VAS will be administered, as needed, if a subject experiences precipitated withdrawal following administration of CAM203 q1w.
- ee Subjects will be discharged on Day 14, if medically acceptable.

Version: 2.0, 17NOV2015 Page 40 of 99

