### 7. INVESTIGATIONAL PLAN

# 7.1. Overall Study Design and Plan

This is a multi-site, randomized, double-blind, repeat-dose Phase 2 study to evaluate the degree and duration of action of multiple doses of CAM2038 q1w in blocking the effects of a mu opioid agonist (hydromorphone) in patients with moderate or severe opioid use disorder. The study will involve 4 phases: Screening, Qualification, Treatment, and Follow-up.

Within 4 weeks of initiating screening, subjects will be admitted to a clinical research unit (CRU) for the Qualification Phase. Following check in to the CRU, subjects will be transitioned to a short-acting oral opioid, IR morphine 30 mg, (administered 4 times daily [QID]), for a minimum of 3 days and a maximum of 7 days (Qualification Phase described in detail in Section 7.1.2). One additional dose of IR morphine 30 mg may be administered for the first 3 days of stabilization, as needed, at the investigator's discretion. After stabilization on IR morphine 30 mg, all subjects will complete a 3-day Qualification/Baseline Hydromorphone Challenge Session which will involve IM administration of 3 doses of hydromorphone (Treatment A: 0 mg [placebo], Treatment B: 6 mg and Treatment C: 18 mg) administered once daily (Day -3, Day -2, and Day -1) in a randomized, double blind, crossover manner, with each hydromorphone administration separated by approximately 24 hours (described in detail in Section 7.1.4).

Following the Qualification/Baseline Hydromorphone Challenge Session, eligible subjects will receive CAM2038 q1w at doses of 24 mg or 32 mg (randomized in a 1:1 ratio to 1 of 2 groups). Subjects will receive once weekly SC injections of CAM2038 q1w for 2 weeks (injections on Day 0 and Day 7) and will remain inpatient in the CRU for up to 25 days (including Qualification Phase), during which time 4 Hydromorphone Challenge Sessions (3 consecutive days each) will be conducted on Days 1 to 3, Days 4 to 6, Days 8 to 10, and Days 11 to 13, respectively. Safety and pharmacodynamic assessments will be performed on each day of the Hydromorphone Challenge Sessions at multiple timepoints beginning at pre-dose until approximately 5 hours post-dose. Plasma samples to quantify BPN and norbuprenorphine levels will also be obtained approximately 60 minutes prior to hydromorphone dosing on each day of the Hydromorphone Challenge Sessions.

Subjects will be discharged on Day 14 and a follow-up phone interview will be conducted on approximately Day 21.

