## 10.4.1.1. Adverse Event Reporting

All AEs (except for withdrawal symptoms, see below) must be entered on the AE CRF, regardless of causality or severity. AEs include new AEs, worsening baseline conditions, clinically significant laboratory findings, disease-related signs and symptoms that were not present at baseline, and any events or findings that the Investigator feels are clinically significant. Withdrawal symptoms will be captured via specified assessments and should not be recorded as AEs.

Disease-related signs and symptoms that are present at baseline should not be recorded as AEs unless they worsen in severity or increase in frequency, but rather should be considered and recorded as pre-existing conditions.

Information collected concerning AEs will include the following:

- Name of the event
- Onset date
- Resolution date
- Severity (i.e., mild, moderate, or severe)
- Relationship to study drug
- Action and outcome
- Seriousness of event

All AEs will be documented and followed from the time the subject has signed the ICF until 14 days after the Follow-up Visit (or 30 days after Early Termination). Serious AEs and AEs that have been designated as possibly related to study drug will be followed until resolution or stabilization. At least 3 attempts will be made to contact the subject and after 3 unsuccessful attempts, a certified letter will be sent to the subject address that was provided to the site.

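### The Day 21 call is meant to obtain withdrawal effects, but no withdrawal measure is scheduled that day and the AE rule bars entering withdrawal as an adverse event

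*Protocol*

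**What the plan says.** Protocol Section 7.1 sets the timing: "Subjects will be discharged on Day 14 and a follow-up phone interview will be conducted on approximately Day 21". Section 7.1.5 gives the call its purpose, which expressly includes withdrawal: a "telephone interview will be conducted approximately 7 days after discharge from the CRU to obtain information on any safety issues including withdrawal effects". It adds that after Day 14 "plasma BPN levels are expected to be approximately 1.4 to 1.8 ng/mL and to gradually taper off", so that immediate withdrawal at discharge is not expected.

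The Day 21 column of Table 4 has two marks: concomitant medications/procedures and adverse events. The COWS and OOWS rows are last marked at Day 14/ET; on challenge days footnote t states that "COWS and OOWS will be administered prior to dosing on each Hydromorphone Challenge Session day". The withdrawal severity VAS is marked on Days 0 and 7 only, and footnote dd limits it: "Severity of Opioid Withdrawal VAS will be administered, as needed, if a subject experiences precipitated withdrawal following administration of CAM203 q1w". Section 10.6.2 adds COWS, OOWS and the VAS only when withdrawal follows a CAM2038 injection, every 4 hours while awake for at least 24 hours after dosing.

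Section 10.4.1.1 says: "Withdrawal symptoms will be captured via specified assessments and should not be recorded as AEs". Its opening sentence makes the same exception for the AE CRF. AE documentation runs to 14 days after follow-up, so the exception is in force on Day 21.

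SAP Section 9.2 summarises withdrawal scales only on the days they are scheduled. SAP Appendix A lists no table or listing for the follow-up call.

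**The concern.** Each rule is reasonable alone. Keeping withdrawal out of the AE tables avoids double counting when a scale is being taken. COWS and OOWS need direct observation (pulse, pupils, gooseflesh, a timed 5-minute watch), so they cannot be done by telephone. Together, however, the rules leave the call with a stated task and nowhere defined to put the answer.

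Subjects are physically dependent on opioids at entry, the last injection is on Day 7, and the call is the only scheduled contact after discharge. One secondary objective is safety and tolerability. What subjects report about withdrawal after leaving the unit could not be summarised by dose group, and an empty output would reflect the recording rule as much as what subjects experienced.

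**Working it through.** The main point rests on the text; the protocol states no figure to reproduce.

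**Where could withdrawal reported on Day 21 be recorded?** Table 4 has 10 visit columns.
- COWS: marked in 9 of 10; Day 21 blank.
- OOWS: marked in 6 of 10; Day 21 blank.
- Withdrawal severity VAS: marked in 2 of 10 (Days 0 and 7); Day 21 blank.
- Unscheduled assessments (10.6.2): tied to an injection, and the last injection is 14 days earlier (21 − 7).
- Adverse events: marked on Day 21, but 10.4.1.1 excludes withdrawal symptoms.
- Concomitant medications/procedures: marked on Day 21; would show a treated episode only indirectly.

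So 0 of 3 withdrawal instruments are scheduled, and the one row that could hold a symptom is closed to this one.

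**Would lifting the AE bar be enough?** No. Protocol 12.3.4.1 ends the treatment-emergent window for non-serious AEs at discharge or early termination, so an event starting between Day 14 and Day 21 falls outside it. SAP 11.2 tabulates onsets up to last dose + 30 days, which is Day 37 (7 + 30) for a last dose on Day 7. The same event is in the tables under one document and out under the other.

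**Side check: the expected level after Day 14.** The 1.4 and 1.8 ng/mL in 7.1.5 equal the predicted steady-state troughs for 24 and 32 mg in Table 3, but subjects receive two injections. Inputs are the 7-day level after one dose, C1 (Table 2: 0.86 at 24 mg, 1.1 at 32 mg, 0.61 and 0.58 at 16 mg, mean 0.595), and the steady-state trough, Css (Table 3: 1.4, 1.8, 0.84). Assume linear PK and mono-exponential carry-over, r = 1 − C1/Css.
- r = 1 − 0.86/1.4 = 0.386 (24 mg); 1 − 1.1/1.8 = 0.389 (32 mg); 1 − 0.595/0.84 = 0.292 (16 mg, the only dose with an observed steady state).
- Day 14 as C1(1 + r): 24 mg, 0.86 × 1.292 = 1.11 to 0.86 × 1.386 = 1.19; 32 mg, 1.1 × 1.292 = 1.42 to 1.1 × 1.389 = 1.53.
- Day 14 as Css(1 − r²) with the 16 mg r: 1.4 × (1 − 0.085) = 1.28; 1.8 × (1 − 0.085) = 1.65.
- Range: about 1.1 to 1.3 ng/mL (24 mg) and 1.4 to 1.65 ng/mL (32 mg), which is 8.5% to 21% below the stated values, depending on method.
- Day 21 is r times Day 14, a fall of 1 − r, or 61% to 71%, to about 0.32–0.46 ng/mL (24 mg: 0.292 × 1.11; 0.386 × 1.19) and 0.41–0.59 ng/mL (32 mg: 0.292 × 1.42; 0.389 × 1.53).

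A second route agrees. A log-linear decline at 32 mg from 3.76 ng/mL at 36 h (Table 1) to 1.1 at 168 h (Table 2) gives a half-life of 132 × ln 2 / ln(3.76/1.1) = 74 h. That takes 1.4 and 1.8 ng/mL to about 0.3 and 0.4 by Day 21, or 0.2 to 0.7 for half-lives of 60 to 120 h. The call therefore falls while the depot is wearing off.

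**The case against.** The best defence is that the interview is itself a specified assessment: 7.1.5 orders it and names withdrawal as content, and the CRF and Manual of Procedures, which are not among the documents, may contain a field for it. That is possible. But neither the protocol nor the SAP defines an item, a Table 4 row or an output for it, and footnote q records only spontaneously reported AEs.

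A reader might infer more than the documents support:
- That the information is lost altogether. Source notes, the Day 21 concomitant medication entry, or an SAE report after a hospitalisation may hold it. The text does not say whether the withdrawal exception gives way to SAE reporting, or to the clause counting findings the investigator thinks clinically significant.
- That the call is the only look at withdrawal while buprenorphine falls. Levels also fall within each dosing interval (at 32 mg, from a single-dose peak of 5.3 to 1.1 ng/mL at 7 days), and COWS and OOWS are taken through those declines and at Day 14. Only the decline after discharge is unmeasured.
- That an empty table would be presented as good tolerability of stopping. No objective, endpoint or planned claim concerns stopping.
- That the steady-state figure undermines the statement about discharge. That statement is approximate and concerns only immediate withdrawal. Section 9.4 describes a depot giving under 2 ng/mL as effective for withdrawal suppression. The gap is also smaller than the geometric CV of the 7-day level (22% to 26% in Tables 2 and 3), and the Day 14 level is measured directly.

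**Conclusion.** The inconsistency between 7.1.5, Table 4 and 10.4.1.1 stands. It is a stated exclusion, not merely missing detail, and it applies to every subject called: withdrawal emerging after Day 14 discharge has no defined place to be recorded or analysed. This takes the protocol and SAP at their word and assumes that no CRF field outside them fills the gap. Its reach is limited to post-discharge safety information; primary and secondary efficacy results are untouched.

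The exposure figure is a minor labelling matter. It depends on the PK assumptions above and does not by itself change the conclusion about immediate withdrawal at discharge.

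**What to change.** Change data capture only, by one of two routes.

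1. Add the existing Table 6 opioid withdrawal severity item (0 to 100), asked verbally, to the Day 21 column of Table 4, and add a SAP table or listing by CAM2038 group. Cost: one CRF item and one output. A verbal rating is not strictly comparable with the paper scale, and it describes the time of the call, not an episode that has already settled.
2. Limit the bar in 10.4.1.1 to days with a scheduled withdrawal assessment, so that withdrawal reported at the call is entered as an AE with onset date and severity. This route also requires aligning the TEAE windows in protocol 12.3.4.1 and SAP 11.2 so that these events are tabulated. Cost: a few more AEs and one reconciled definition.

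Neither route adds a visit. Separately, label the 1.4 to 1.8 ng/mL in 7.1.5 as a steady-state prediction, or restate it for two injections with its assumptions.
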